##### NINDS-CDE Recommended Assessments for PD-Specific Clinical Features (only for on-state)

1. Demographics
2. PD Medical History
3. PD Family History
4. PD and Non-PD Medication Log
5. Motor: MDS-UPDRS parts I-IV
6. Psychiatric: Structured clinical interview for DSM-IV-TR (SCID) axis I disorders, research version, non-patient edition (29)
7. Cognitive: Montreal Cognitive Assessment (MoCA)(31)
8. Other non-motor: Non-motor Symptoms Questionnaire (NMS-Quest)(35) and the Scales for Outcomes in Parkinson's disease autonomic dysfunction scale (SCOPA-AUT)(32,33)
9. Quality of life: 8-item Parkinson's Disease Questionnaire (PDQ-8)(34)
10. Questionnaire for Impulsive-Compulsive Disorders in Parkinson's Disease(QUIP)(47)

11. Neo Five-Factor Inventory(48)

12. Rapid Assessment of Physical Activity(RAPA)(49)

For objective 2:

The intervention will be 8 weeks in duration and include a 4-week dosage titration period and a 4-week maintenance period. Transdermal patch. Dosing will begin at baseline on day zero with either 1) placebo or 2) rotigotine at 2mg/24h and will be increased following the recommended dose escalation schedule for PD such that subjects will increase to 4mg/24hrs in week 2, and 6mg/24hrs in week 3. This dose of rotigotine is within the range shown to be safe and efficacious for the treatment of motor symptoms. 17,36,37) The timing of assessments is shown in Table 1. All assessments except for the physical exam, and the Clinical Global Impression for Anxiety Severity and change scales (CGI-S and CGI-C)(38) are part of the CAPSIT-PD on- and off-state testing battery, the table indicates administration points. Safety and tolerability will be assessed by recording adverse events.

b. Study duration and number of study visits required of research participants.

Objective 1 is one 3-hour cross-sectional visit, duration and visits for objective 2 are in Table 1

Table 1. Assessment schedule for objective 2					
Visit Number	Screening	Baseline	Follow-up visits		
Time	- - -	0	WK2	WK4	WK8: FINAL
Diagnostic Interview or AIM 1 Battery	X				X
Physical Examination	X				X
MDS-UPDRS I-IV	X				X
MoCA	X				X
CGI-Severity	X	X			
CGI-Change			X	X	X
HAM-A	X	X	X	X	X
HAM-D	X	X	X	X	X
SCOPA-AUT, NMS	X	X	X	X	X

c. Blinding, including justification for blinding or not blinding the trial, if applicable.

For the clinical trial in objective 2: double-blinded, randomized, placebo controlled, 8-week intervention study of rotigotine vs. placebo for the treatment of anxiety in PD. The study is double-blinded to reduce the risk of bias in rating anxiety response to treatment as both the subject and investigators will be rating anxiety using self-reports and investigator-administered scales.

d. Justification of why participants will not receive routine care or will have current therapy stopped.

Patients will receive routine care and will NOT have current therapy stopped.

e. Justification for inclusion of a placebo or non-treatment group.

Absence of current standard treatment for anxiety in PD justifies inclusion of a placebo group. Anti-anxiety drugs based on serotonin, norepinephrine, and benzodiazepine mechanisms are the current standard in non-PD populations and are used in PD without sufficient evidence of efficacy and may be associated with side effects.

f. Definition of treatment failure or participant removal criteria.

Rotigotine is an evidence based treatment for motor symptoms and motor complications of treatment in PD and deemed to be of "acceptable risk without specialized monitoring".(17) Rotigotine does carry the risk of nausea, vomiting, application site reactions, dizziness, anorexia, hyperhidrosis, insomnia, lower extremity edema, somnolence and dyskinesia. Rotigotine is a treatment routinely used as part of clinical care in PD. If impulse control disorders occur the subject will taper and stop the study drug, their treating neurologist will be notified, and they will be referred for psychiatric treatment. Subjects will be examined for lower extremity edema at screening and at each follow-up visit. If edema occurs subjects will be asked if they wish to discontinue the study drug. Subjects will be asked about excessive somnolence at each visit. If somnolence is severe and interferes with daily functioning, tapering and discontinuation of the study drug will be recommended.

Subjects in the intervention study will be medically screened prior to enrollment and will be monitored at the designated intervals for any adverse events. Subjects who are acutely suicidal or an imminent risk to themselves will be excluded. Subjects will be removed from the study if they request removal, if the team believes it is unsafe to continue, if they experience significant distress for any reason, or if the patient becomes imminently suicidal. Subjects will be monitored closely by an experienced clinical team, available 24-hours per day.

g. Description of what happens to participants receiving therapy when study ends or if a participant's participation in the study ends prematurely.

After termination of the intervention study, prematurely or scheduled, a summary letter will be sent to the patient's treating clinicians detailing the patient's participation in the study, the patient's response, aftercare plans, and any other relevant information. The study medication or placebo will be tapered and stopped, unless, in the case of participant on study drug, their treating doctor wishes to continue rotigotine and take over prescribing it as part of their routine care. Subjects will be offered follow-up psychiatric care in our clinic as well as assistance in obtaining care elsewhere, including by providing consultation to their primary clinician/neurologist. All adverse events will be reported to the JHH IRB.

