## 6. Drugs/ Substances/ Devices

- a. The rationale for choosing the drug and dose or for choosing the device to be used.

Rotigotine is an evidence-based treatment for motor symptoms and motor complications of treatment in PD and deemed to be of "acceptable risk without specialized monitoring". Dosing will begin at baseline on day zero with either 1) placebo or 2) rotigotine at 2mg/24hrs and will be increased following the recommended dose escalation schedule for PD such that subjects will increase to 4mg/24hrs in week 2, and 6mg/24hrs in week 4.]\* This dose of rotigotine is within the range shown to be safe and efficacious for the treatment of motor symptoms in PD.

- b. Justification and safety information if FDA approved drugs will be administered for non-FDA approved indications or if doses or routes of administration or participant populations are changed.

N/A

- c. Justification and safety information if non-FDA approved drugs without an IND will be administered.

N/A

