For objective 2: The primary outcome variable is the HAM-A. Power was calculated based on an enrollment of 60 subjects total, equally distributed between treatment and control groups, with a 10% dropout by the final time-point, and a standard deviation of 8.55 (which is a pooled estimate calculated from different anxiety subtypes in PD patients assessed using the HAMA).(43) The within subject/between time-point correlation was assumed to be 0.5 with a compound symmetric correlation structure, and the alpha level was set at .05. Power calculations were based on the formula of Jung and Ahn,(44) which calculates power for the difference in slope (i.e. the difference in response trajectory) between treatment and control groups for a longitudinal clinical intervention. Based on the assumptions specified, we would be able to detect an effect size of .69 from baseline to 8 weeks for the two groups with 80% power. This proposal is for a proof of concept study that will provide important initial estimates which may be used to 1) assess the potential efficacy of this novel anxiety intervention and thus provide necessary data for a "go-no-go" decision for a more definitive hypothesis-testing trial, and 2) provide estimates of effect size and variance needed to properly design such a trial.

Screening for objective 1: Screen failures are expected to be rare for objective 1 as there are only 3 criteria for exclusion: 1) UK Brain Bank criteria for PD, 2) English speaking, and 3) nondemented. In our longitudinal study of Parkinson's disease, which has autopsy confirmation at study end, the rate of accurate clinical diagnosis of PD is approximately 90%. The presence of dementia has a similar accuracy and will be further screened using the MoCA with a cut off of <23. The drop-out rate is also expected to be low as objective 1 takes place in one 3-hour visit. Screening for objective 2: Objective 2 will require 60 subjects who *can* be recruited from the n=200 from objective 1. Based on our preliminary data, 30% of subjects with a DSM anxiety disorder and comorbid depression and up to 53% with anxiety disorders only will not be

on any treatment for anxiety. In addition, we have included a protocol for enrolling individuals whose anxiety is not adequately controlled on their current therapy.(item 4 inclusion criteria)

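### Sections 4a and 6a put the step to 6 mg/24h in different weeks (3 and 4), so exposure at the WK4 assessment is not defined

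*Combined protocol and SAP*

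**What the plan says.** Objective 2 is an 8-week double-blind comparison of rotigotine with placebo. Its dosing is described twice.

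- **Section 4a (Study Procedures, objective 2):** "Dosing will begin at baseline on day zero with either 1) placebo or 2) rotigotine at 2mg/24h". Then "subjects will increase to 4mg/24hrs in week 2, and 6mg/24hrs in week 3".
- **Section 6a (Drugs/Substances/Devices):** the same start, then "subjects will increase to 4mg/24hrs in week 2, and 6mg/24hrs in week 4".

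Both sections say that they follow a recommended escalation schedule (in 6a, the dose "will be increased following the recommended dose escalation schedule for PD such that" the steps occur), but that schedule is not reproduced. Section 4a adds that the 8 weeks "include a 4-week dosage titration period and a 4-week maintenance period", without naming the week in which the last step falls.

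Table 1 (section 4b) places follow-up visits at WK2, WK4 and WK8, with HAM-A scored at each. On safety, section 4a says "Safety and tolerability will be assessed by recording adverse events", and section 4f says "Subjects will be examined for lower extremity edema at screening and at each follow-up visit". Section 7c bases power on a difference in slope between arms and states that the trial can "detect an effect size of .69 from baseline to 8 weeks for the two groups with 80% power".

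**The concern.** The two sections give different instructions for the same dose step, and both are current text. A site following one departs from the other. Section 8c requires deviations to be compiled and reported to the IRB, yet staff cannot tell which schedule would be the deviation.

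The statistical stake is the WK4 assessment. HAM-A is the primary outcome, and under a slope comparison the WK4 value contributes to the estimate. How long an active-arm subject has been at the top step by then depends on which section was followed. If subjects were handled differently, the active arm would mix two regimens at that visit. That is a risk; the document does not show that it happened. A safety finding at WK4 would also be hard to relate to dose and time at dose. Section 7c wants effect-size and variance estimates for designing a later trial, and those should refer to a defined regimen.

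**Working it through.** The plan states no figure for time at each dose, so there is none to reproduce. The check compares the two sections and counts days.

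**Inputs.** Start at 2 mg/24h on day 0 and step to 4 mg/24h in week 2 (both sections). Step to 6 mg/24h in week 3 (4a) or week 4 (6a). WK4 is taken as day 28 and WK8 as day 56 (Table 1).

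**Assumption.** The document does not say what *in week k* means in days, so two readings are used:

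- Reading A: week k starts on day 7(k-1).
- Reading B: week k means day 7k, as the visit labels suggest.

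**Formulas.** Let d4 and d6 be the days of the steps to 4 and 6 mg/24h. Days at 4 mg/24h = d6 - d4. Days at 6 mg/24h by day T = T - d6.

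| | A, section 4a | A, section 6a | B, section 4a | B, section 6a |
|---|---|---|---|---|
| d4 | 7 | 7 | 14 | 14 |
| d6 | 14 | 21 | 21 | 28 |
| Days at 4 mg/24h | 14-7 = 7 | 21-7 = 14 | 21-14 = 7 | 28-14 = 14 |
| Days at 6 mg/24h by WK4 | 28-14 = 14 | 28-21 = 7 | 28-21 = 7 | 28-28 = 0 |
| Days at 6 mg/24h by WK8 | 56-14 = 42 | 56-21 = 35 | 56-21 = 35 | 56-28 = 28 |

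Nominal cumulative dose to day 28, as 2 × days + 4 × days + 6 × days:

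- A, 4a: 2×7 + 4×7 + 6×14 = 126 mg
- A, 6a: 2×7 + 4×14 + 6×7 = 112 mg
- B, 4a: 2×14 + 4×7 + 6×7 = 98 mg
- B, 6a: 2×14 + 4×14 + 6×0 = 84 mg

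Within each reading the sections differ by 7 days at the top step and by 14 mg. Under reading B of section 6a, the WK4 visit falls on the day of the step, so WK4 HAM-A would reflect no time at the top dose.

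**Could different week counts reconcile the sections?** Suppose 4a uses day 7k and 6a uses day 7(k-1). The 6 mg steps then coincide (7×3 = 21 and 7×(4-1) = 21), but the 4 mg steps do not (7×2 = 14 against 7×(2-1) = 7). The mismatch moves to the earlier step.

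**Does the four-plus-four-week split settle it?** No. The plan does not say whether titration includes a hold at 6 mg/24h. With such a hold, either schedule can fit.

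**Visits.** Table 1 has no week-3 visit. Under A the 6 mg step falls on WK2 (day 14) by 4a and on day 21, between visits, by 6a. Under B it falls on day 21 by 4a and on WK4 (day 28) by 6a.

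**Power.** Section 7c uses sample size, dropout, standard deviation, correlation and alpha. No dosing input enters, so the stated power does not depend on this point.

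**The case against.** The strongest reply is that this is a drafting slip with little effect. Start, first step and top dose agree. Power is untouched, and the effect size is stated from baseline to 8 weeks. Under both readings the top step is reached by day 28, so at least 56-28 = 28 days at that step precede WK8. WK4 is one intermediate visit in a proof-of-concept study. All of that stands, and it limits the size of the problem. It does not remove a contradiction in a drug-administration instruction that the document gives no way to resolve.

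Three further points have some force:

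- The 7-day difference assumes that both sections count weeks the same way and step on the same day of the week. That is correct. The overall spans (0 to 14 days by WK4, 28 to 42 by WK8) combine the contradiction with the undefined week and should not be put down to the contradiction alone.
- Staff working from the recommended schedule that both sections invoke might face no ambiguity. That cannot be judged, because the schedule is not in the document.
- A step between visits is not a defect in itself, and under reading A the 4 mg step falls between visits in both sections. It matters only because patch supply has to match whichever schedule is adopted.

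One could argue that section 4a governs because it is the section on sequence and timing. One could equally argue that 6a is the later text, because its sentence ends with an edit mark like those in Table 2. These cues point in opposite directions, and neither is a statement of precedence.

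**Conclusion.** The concern holds and must be fixed. The two sections contradict each other on the week of the step to 6 mg/24h, and nothing in the document decides between them. With a common week convention the difference is 7 days: 7 against 14 days at 4 mg/24h, and at the top step 14 against 7 (or 7 against 0) days by WK4 and 42 against 35 (or 35 against 28) by WK8. These figures rest on the two assumed readings of a study week and on WK4 and WK8 being days 28 and 56. The consequence is an undefined regimen at an assessment of the primary outcome. The nominal top dose at WK8, the stated power and the sample size are not in question.

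**What to change.** The sponsor should reconcile sections 4a and 6a so that both give one schedule, and define study weeks in days, with the same definition for dose steps and visits. The protocol should state how the steps map to the 4-week titration and 4-week maintenance periods, including whether titration contains a hold at the top step. Any dispensing instructions for active and placebo patches should be checked against that schedule, including for a step that falls between visits. Which schedule is right is for the sponsor to decide; none is proposed here.

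The cost is a one-line correction in one section, a one-line definition of study weeks, a sentence on the two periods and a check of the dispensing instructions. Sample size, visits and analysis do not change.

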#### 4. Study Procedures

- a. Study design, including the sequence and timing of study procedures (distinguish research procedures from those that are part of routine care).

For objective 1: Subjects will be assessed in both the “on” and “off” motor states following the clinical protocol from the Core Assessment Program for Surgical Interventional Therapies in PD (CAPSIT-PD).(23) We use the CAPSIT-PD protocol routinely in the PDRC and movement disorder clinics and will include consenting individuals as part of this study. However, a portion of the subjects recruited will have the CAPSIT-PD protocol exclusively for this study and not as a part of routine clinical care. "Wearing-off" and the "off-motor state" in PD are defined as a generally predictable recurrence of motor and non-motor symptoms as the effect of dopaminergic medications stops.(12) Subjects will temporarily stop all dopaminergic medications for a minimum of 12-hours in order to be assessed in the “off” motor state in the morning. (Most individuals with PD do not take medications overnight and usually take their last dose between 5-9pm. Therefore most participants will only be off medications for a few hours more than they normally would be as the study will be conducted in the morning) The on- and off-state assessments are listed below. Subjects will then take their usual morning dopaminergic medications and after one hour, to allow them to return to their best "on" state, repeat the CAPSIT-PD on-off battery. In addition to the on-off testing battery, several PD-related clinical features will be assessed, only in the on-state, using instruments recommended by the National Institute of Neurological Disorders and Stroke Common Data Element Project (NINDS-CDE)(24) for PD.

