## 5. Inclusion/Exclusion Criteria

Subjects for both objectives will be English-speaking adult men and women including minority groups, ages 21 years or older, with idiopathic PD, based on UK Brain Bank Criteria.(39) Subjects with a diagnosis of dementia or a Montreal Cognitive Assessment (MoCA) (30) <23 will be excluded to reduce the chance of enrolling individuals with Lewy body dementia. Additional inclusion and exclusion criteria for objective 2 are in Table 2.

Table 2. Additional inclusion and exclusion criteria for objective 2 8-week intervention study
---

Inclusion Criteria
--------------------

1. Diagnosis of DSM Anxiety Disorder and as part of this intervention study, we will include all anxiety subtypes provided treatment with medication is indicated in standard clinical psychiatric practice
2. Stable medical history and general health. If non-postmenopausal female, must be non-pregnant and using a medically acceptable form of contraception during the study if sexually active
3. On stable anti-parkinsonian therapy for 2 weeks before enrollment and expected to be able to remain on stable therapy for the 8-week study.
4. If treated for depression, must be on stable anti-depressant for 2 weeks before enrollment and expected to be able to remain on stable therapy for the 8-week study.
5. \*[Not on anti-anxiety therapy (unless it is for another indication, i.e. REM Sleep Behavior Disorder) at time of enrollment OR able to be tapered safely off these medications as determined by the t ½ of prescribed medication at the time of screening]\*

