## 8. Risks

a. Medical risks, listing all procedures, their major and minor risks and expected frequency.

All members of the research team will make every effort to implement the protocol procedures in a sensitive and supportive manner. Only subjects who are medically stable will participate in these studies. [name] will provide close clinical monitoring during all aspects of the study.

Clinical assessments and questionnaires: Subjects will be informed prior to beginning the evaluation to please notify the examiner if they experience any distress. If this occurs, the examiner will stop the evaluation. To minimize the chance of this happening, subjects will be provided breaks and positive feedback and research staff will provide assistance with form completion if needed. We will conduct psychiatric and motor assessments in a standardized fashion. These approaches are standard for patient assessment in clinical practice and are generally not associated with more severe complications. Frequency: rare

On- and off-motor state testing: As mentioned above we will follow the standard clinical protocol established in the Core Assessment Program for surgical Interventional Therapies in PD.(66) Subjects will be closely monitored for discomfort or distress. For subjects who experience distress the off-state testing will be stopped and their usual Parkinson's medications will be resumed. For subjects unable to tolerate the full 12 hour off-state, it is recommended that the longest tolerable wash-out be determined and to use this period for all subsequent assessments. For our study, subjects who fail to tolerate washout of 8 hours or more will be excluded to minimize the potential for patient distress while preserving the goal of optimal washout of dopaminergic medication. Frequency: rare

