Rotigotine drug treatment: Rotigotine carries the risk of impulse control disorders, lower extremity edema, and excessive somnolence. Prior to enrollment in the intervention study subjects will be screened for impulse control disorders and subjects with any current or past impulse control disorders will be excluded from the study. During the course of the study subjects will be specifically asked about impulse control disorders at each visit. If impulse control disorders occur the subject will taper and stop the study drug, their treating neurologist will be notified, and they will be referred for psychiatric treatment. Subjects will be examined for lower extremity edema at screening and at each follow-up visit. If edema occurs subjects will be asked if they wish to discontinue the study drug. Subjects will be asked about excessive

daytime somnolence at each visit. If daytime somnolence is severe and interferes with daily functioning, tapering and discontinuation of the study drug will be recommended.

Subjects in the intervention study will be medically screened prior to enrollment and will be monitored at the designated intervals for any adverse events. For females of childbearing age, negative urine pregnancy test prior to study will be required. Subjects who are acutely suicidal or an imminent risk to themselves will be excluded. Subjects will be removed from the study if they request removal, if the team believes it is unsafe to continue, if they experience significant distress for any reason, or if the patient becomes imminently suicidal. Subjects will be monitored closely by an experienced clinical team, available 24-hours per day.

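### Section 4d says no current therapy will be stopped, but the plan stops two kinds, and the anti-anxiety taper has no risk entry and no inadequate-control condition

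*Combined protocol and SAP*

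**What the plan says.** The prompt at section 4d asks for a justification if participants will be denied routine care or have current therapy stopped. The answer is "Patients will receive routine care and will NOT have current therapy stopped". It is not limited to one drug class or one objective.

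Two other parts of the plan bear on this:

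- **Objective 2.** Table 2 inclusion item 5 (section 5) accepts subjects who are not on anti-anxiety therapy at enrollment, with an exemption for drugs given for another indication. Its alternative is that they are "able to be tapered safely off these medications", judged at screening from the drug's half-life.
- **Objective 1.** Section 4a says "Subjects will temporarily stop all dopaminergic medications for a minimum of 12-hours", and adds that for a portion of subjects this testing is done only for the study and not as clinical care.

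Section 8a carries the prompt "Medical risks, listing all procedures, their major and minor risks and expected frequency". The answer has three headed groups: assessments, on/off testing and rotigotine treatment.

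Section 7c describes the route for already-treated subjects as one for people whose anxiety their present treatment does not control, and points to inclusion item 4.

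**The concern.** Someone judging participant protection would look first at 4d and 8a. From those two sections alone they would conclude that nobody loses a current anti-anxiety treatment to enter the trial. Table 2 says that some may, and that they then have an even chance of placebo for 8 weeks.

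The eligibility rule is also looser than the plan's own description of it. Item 5 asks whether a taper would be safe. It does not ask whether the present treatment is failing. What is at stake is protection of participants and a single consistent entry rule. The estimate of treatment effect is not in question.

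**Working it through.** The plan gives no figure to reproduce here, so the check is a comparison of text with one line of arithmetic.

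**1. Does item 5 involve stopping therapy?** Its two limbs are alternatives: not on anti-anxiety therapy, or able to come off it. The second limb serves no purpose unless the drug is then withdrawn. Apart from the other-indication exemption, a subject taking such therapy can enter only by stopping it.

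**2. Is the taper part of the study?** Item 5 places the judgement at screening, and 7c says screening follows consent. The sequence points to a taper done for study entry.

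**3. Can 4d be read so that it is true?**

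| Reading of 4d | Anti-anxiety taper (objective 2) | Dopaminergic stop (objective 1) |
|---|---|---|
| As written | conflicts | conflicts |
| Antiparkinsonian drugs only | no conflict | conflicts |
| Objective 2 only | conflicts | no conflict |

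Only both restrictions together would rescue the statement, and the text contains neither.

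**4. Does 8a cover each interruption?**

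- *Dopaminergic washout:* yes. If a subject is distressed, testing stops and the usual medication is resumed. There is also a tolerance limit: "subjects who fail to tolerate washout of 8 hours or more will be excluded to minimize the potential for patient distress".
- *Anti-anxiety taper:* no. The tapering in 8a is of the study treatment, for impulse control disorders and for severe somnolence ("tapering and discontinuation of the study drug will be recommended").

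**5. Does Table 2 require inadequate control?** No. Item 1 requires a DSM anxiety disorder and admits all subtypes "provided treatment with medication is indicated in standard clinical psychiatric practice". A patient doing well on medication could satisfy both parts. Item 4, to which 7c points, concerns antidepressant stability. None of the 5 inclusion and 8 exclusion items states the 7c condition.

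**6. What follows the taper?** Objective 2 allocates 30 to rotigotine and 30 to placebo, so the chance of placebo is 30 / (30 + 30) = 0.50, for 8 weeks.

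**The case against.** The strongest reply is that the plan already contains most of the substance and that only cross-referencing is missing. Much of this stands, and it rules out several stronger readings.

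- *A reader might infer that the taper has no rationale anywhere.* That is not so. Section 4e says conventional anti-anxiety drugs are used in PD on insufficient evidence and may cause side effects. The background describes falls, confusion and worse tremor. The gap is that 4d denies the taper and therefore does not draw on this.
- *A reader might infer that every user of a conventional agent would be tapered.* Section 4e does say "Anti-anxiety drugs based on serotonin, norepinephrine, and benzodiazepine mechanisms are the current standard in non-PD populations", and those are the classes that could be involved. But item 4 keeps subjects treated for depression on a stable antidepressant, and item 5 exempts drugs given for other indications. The exposed group is narrower.
- *A reader might infer a headcount from 7c.* There, 30% of subjects with comorbid depression and up to 53% with anxiety only are untreated, leaving 100 − 30 = 70% and at least 100 − 53 = 47% treated. Multiplying by 60 gives roughly 28 to 42. This does not estimate the number tapered: the case mix is not given, exemptions apply, and untreated subjects may be recruited first.
- *A reader might infer that well-controlled patients will be taken off treatment.* Table 2 permits it, but item 1, the safe-taper wording and the intent stated in 7c make it less likely. Nothing shows that it would occur.
- *A reader might infer that nothing is in place if anxiety worsens.* Medical screening, removal for distress or safety, a clinical team on call around the clock and an offer of psychiatric follow-up are all stated. HAM-A and CGI-Severity are scheduled at both Screening and Baseline. What is missing is an entry and a rule specific to the taper.

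None of this makes 4d correct or puts the taper into 8a. Consent pages were removed from the text available, so nothing can be said about what participants are told.

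**Conclusion.** The point holds. Section 4d is wrong as written on two counts: the objective 2 anti-anxiety taper and the objective 1 dopaminergic stop. Section 8a covers the second and omits the first. The missing inadequate-control condition in item 5 is the weakest of the three parts. It is a gap between stated intent and the operative rule, not a demonstrated hazard.

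The size cannot be given. The documents do not say how many subjects would be tapered, or how many of those would be well controlled; either number may be zero. The one firm figure is the 50% chance of placebo, which is simply the allocation ratio. A reader might infer an effect on bias, power or sample size; nothing here supports one and none is claimed.

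The conclusion assumes that item 5 means the taper is carried out and that it follows consent, as the screening text indicates. Correction should be made because the error is in the sections that describe participant protection and is cheap to remove.

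**What to change.** - **4d.** State both interruptions, the anti-anxiety taper and the dopaminergic stop, and justify them. For the taper, cite the rationale already in 4e and the background. Amending 4d for the taper alone would leave it inaccurate.
- **Item 5, taper limb.** Add: *and, in the investigator's judgement, the anxiety remains inadequately controlled on that therapy*. Support the judgement with the diagnostic interview, HAM-A and CGI-Severity. No HAM-A threshold is proposed. Keep antidepressants covered by item 4, and drugs for other indications, exempt.
- **8a.** Add a taper entry giving withdrawal and relapse risk, expected frequency, who supervises, and a rule to stop the taper and resume therapy, parallel to the off-state rule.
- **7c (minor).** Clarify the pointer to item 4. It may be a slip for item 5, or may refer to subjects still anxious on a stable antidepressant.

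The cost is mostly wording, since Table 1 already schedules those three assessments at Screening. Supervising the taper may need a contact between Screening and Baseline, where Table 1 shows no visit. The eligible pool becomes somewhat smaller, by an amount the documents do not allow one to estimate.
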